**Table 11 Maintenance Dose of Epoetin Beta Pegol**

Dose step	1	2	3	4	5	6	7
Epoetin beta pegol (once every 4 weeks)	25 µg	50 µg	75 µg	100 µg	150 µg	200 µg	250 µg

**Table 12 Dose Adjustment Algorithm (Epoetin Beta Pegol)**

Hgb (g/dL)	Hgb increase over 4 weeks (g/dL)	Treatment
>13.0	NA	Interrupt treatment until Hgb decreases to less than 12.5 g/dL Resume treatment at the one lower dose level (resume treatment at 25 µg if interrupted at 25 µg)
12.5-13.0	NA	One-step dose reduction
11.5-<12.5	>2.0	One-step dose reduction
	≤2.0	Continue treatment at the current dose level
7.5-<11.5	>2.0	One-step dose reduction
	1.0-2.0	Continue treatment at the current dose level
	<1.0	One-step dose increase
<7.5	NA	Discontinue treatment permanently * and initiate another appropriate treatment

\*: If an initial Hgb value is less than 7.5 g/dL, measurement will be repeated at the same study visit (using the same sample) to calculate the average. If the average meets the Hgb stopping criteria, study treatment will be permanently discontinued.

## 6.5. Blinding

This is an open-label study.

## 6.6. Packaging and Labeling

The contents of the label will be in accordance with all applicable regulatory requirements.

## 6.7. Preparation/Handling/Storage/Accountability

- No special preparation of study treatment is required.
- Only subjects enrolled in the study may receive study treatment and only authorized site staff may supply or administer study treatment. All study medications must be stored in a secure environmentally controlled and monitored (manual or automated) area in accordance with the labeled storage conditions with access limited to the investigator (or subinvestigator) and authorized site staff.
- Subjects must bring all of supplied study medication bottles of GSK127886 at each study visit. Study staff will collect all of study medication bottles supplied at the previous study visit and supply new study medication bottles.

- The investigator (or subinvestigator), institution, or the head of the medical institution (where applicable) is responsible for study treatment accountability, reconciliation, and record maintenance (i.e. receipt, reconciliation and final disposition records).
- Under normal conditions of handling and administration, study medication is not expected to pose significant safety risks to site staff. GSK will provide a document describing occupational hazards and recommended handling precautions either to the investigator (or subinvestigator) when necessary or upon request of the medical institution.
- Further details are provided in the SRM.

## **6.8. Compliance with Study Treatment Administration**

### **GSK1278863**

Since GSK1278863 is self-administered, compliance with GSK1278863 treatment will be assessed through an interview with subjects at each study visit and recorded in the source document and eCRF. A record of the number of GSK1278863 tablets dispensed to and taken by each subject will be maintained and reconciled with study treatment and compliance records. In addition, the number of GSK1278863 doses dispensed, used, and unused, as well as study treatment start and stop dates will be recorded in the eCRF (the number of doses returned and unreturned will also be recorded separately).

### **Epoetin beta pegol**

Epoetin beta pegol will be subcutaneously administered to subjects at the site. Dosing details will be recorded in the source document and eCRF.

## **6.9. Treatment of Study Treatment Overdose**

There is no specific antidote for overdose with GSK1278863. The expected manifestations of GSK1278863 overdosage include signs and symptoms associated with an excessive and/or rapid increase in Hgb concentration. GSK1278863 is highly protein bound; thus, clearance of GSK1278863 by hemodialysis or peritoneal dialysis is very low and these are not effective methods to enhance the elimination of GSK1278863. GSK1278863 metabolites are, in part, cleared via hemodialysis. In the event of a suspected overdose, it is recommended that the appropriate supportive clinical care be instituted, as dictated by the subject's clinical status. Additionally, subjects should be monitored closely for cardiovascular events, increased heart rate and hematologic abnormalities.

Consult the respective approved Prescribing Information for information on overdose for epoetin beta pegol.

## **6.10. Treatment after the End of the Study**

Since the target disease studied is not life-threatening or severely debilitating and there is the alternative therapy, subjects will not receive any additional treatment from GSK after completion of the study. The investigator (or subinvestigator) is responsible for ensuring that consideration has been given to post-study care of the subject's medical condition.

## **6.11. Concomitant Medications and Non-Drug Therapies**

Concomitant medications, including over-the-counter medications and supplements, taken during the study will be recorded in the eCRF. Drug names and start/stop dates will be recorded for general concomitant medications, while additional details, including dose, route of administration, and dosing frequency, will be recorded for certain medications (e.g., ESAs, iron, anti-hypertensive medications). Further details are provided in the SRM.

### **6.11.1. Permitted Medications and Non-Drug Therapies**

Unless specified as a prohibited medication in Section [6.11.2.](#), all concomitant medications should be considered permitted provided they are not contraindicated for the individual subject concerned.

Regular multivitamins (at recommended daily allowance) and other supplements such as calcium and vitamin D may be used if permitted by the investigator or his/her designee.

CYP2C8 is involved in the primary route of metabolism of GSK1278863. Accordingly, co-administration of GSK1278863 with moderate CYP2C8 inhibitors (e.g., clopidogrel, teriflunomide, deferasirox) should be performed with caution. If one of these medications is started, stopped or the dose is changed, Hgb should be monitored every 4 weeks for 12 weeks using a point-of-care Hgb analyzer.

Antihyperphosphatemic agents containing iron (e.g., ferric citrate hydrate) may be started from Week 4 onwards unless any other antihyperphosphatemic agents are appropriate. Once started, iron-containing antihyperphosphatemic agents must be continued until the end of the study wherever possible.

### **6.11.2. Prohibited Medications and Non-Drug Therapies**

Use of any of the following drugs from screening until 7 days after the last dose of study treatment is prohibited:

- Strong inhibitors of CYP2C8 (e.g., gemfibrozil)
- Strong inducers of CYP2C8 (e.g., rifampin/rifampicin)

## **6.12. Supplemental Iron Therapy**

Supplemental iron therapy will be administered according to the Guidelines for Renal Anemia [The Japanese Society for Dialysis Therapy, 2008] if ferritin is  $\leq 100$  ng/mL and TSAT is  $\leq 20\%$ . The investigator (or subinvestigator) can choose the route of administration and dose of prescription iron.

## **7. Study Assessments and Procedures**

Protocol waivers or exemptions are not allowed with the exception of immediate safety concerns. Therefore, adherence to the study design requirements, including those specified in the Time and Events Table, are essential and required for study conduct.

### **7.1. Time and Events Table**

The time and events tables for the entire study and PK assessment are presented as [Table 13](#) and [Table 14](#), respectively. To allow scheduling flexibility, study visits may occur within a window of  $\pm 7$  days on Day 1 scheduled 4 weeks after screening, within a window of  $\pm 3$  days at Week 4, and within a

window of  $\pm 5$  days for the rest of the study. However, subjects receiving the control epoetin beta pegol every 2 weeks should attend study visits, including those only for study treatment, within a window of  $\pm 3$  days. Visit days are counted from Day 1.

Table 13 Time and Events Table

Phase	Screening	Treatment														Follow-up		
Week	-4	Day 1	4	8	12	16	20	24	28	32	36	40	44	48	52	Early withdrawal 	4 weeks after 52 or withdrawal 	
Permissible range (days)	±7	-	±3	±5	±5	±5	±5	±5	±5	±5	±5	±5	±5	±5	±5	-	±7	
Informed consent	X																	
Inclusion/exclusion criteria	X	X																
Medical history, demography, height, weight	X																	
Registration with IWRS	X	X	X	X	X	X	X	X	X	X	X	X	X	X	X	X	X	
Study medication dispensing 		X	X	X	X	X	X	X	X	X	X	X	X	X				
Study treatment compliance			X	X	X	X	X	X	X	X	X	X	X	X	X	X	X	
Vital signs	X	X	X			X			X			X				X	X	X
Ophthalmology 		↔				↔										↔	↔	↔
ECG	X								X								X	
HemoCue Hgb	X	X	X	X	X	X	X	X	X	X	X	X	X	X	X	X	X	
Hematology	X	X	X	Only Hgb	Only Hgb	X	X	X										
Clinical chemistry	X	X	X			X			X			X				X	X	X
Urinalysis (ND subjects only)	X	X							X							X		X
Pregnancy test (urine or serum hCG) 	X	X	X				X			X			X			X	X	X
Estradiol, FSH 	X																	
PK 						X			X									
Ferritin, TSAT	X	X	X			X			X			X				X	X	
Serum iron, TIBC, UIBC, serum transferrin, hepcidin			X	X			X			X			X			X	X	
iPTH			X							X							X	
HR-QoL			X			X			X							X	X	
Genetics sample 		X																
Adverse event assessment 		↔														↔		
Review Concomitant Medications		↔																

1. In Cohort 1, ESA non-users randomized to the epoetin beta pegol group will start treatment with epoetin beta pegol at a dose of 25 µg once every 2 weeks. For these subjects, specified examinations will be performed every 4 weeks, and no study-related assessments will be necessary at study visits only for study treatment (e.g., Week 2, Week 6) (see Section 6.4.2). It should be noted that subjects receiving epoetin beta pegol once every 2 weeks should attend study visits within a window of ±3 days.
2. If a subject visit the study site only to receive study medication, only registration with the IWRS, study medication dispensing, and study medication compliance will be required.
3. Ophthalmology exams should be conducted at the following time points.

- Screening: anytime after consenting and prior to first dose of study medication (Day 1)
- Week 12: window from weeks 10-14 (inclusive)
- End of study: window from weeks 48-52 (inclusive)
- Early study medication discontinuation: withdrawal eye exam as close to the last dose as possible (the repeat exams are not required if one has been performed within the 2 prior weeks).

4. Performed in females of childbearing potential: serum pregnancy test will be performed if urine pregnancy test is not feasible.

5. Measured in female subjects only to determine the menopausal status (see Section 5.1.)

6. See [Table 14](#).

7. Informed consent for optional Genetic research should be obtained before collecting a sample (see Section 7.6.).

8. See Section 7.4.1.1..

9. For withdrawn subjects, specified assessments should be done wherever possible.

**Table 14    Blood Sampling Schedule for Pharmacokinetics (Only Subjects in GSK1278863 Group)**

PK sample	Week 12 	Week 24 
Blood sampling timing 	1, 2, 3, and 4 h after administration of GSK1278863	

Subjects must take the study medication with regard to blood sampling time. Subjects will record the date and time of the last two study medication doses taken prior to blood sampling in the medication diary. Preferably, there should be an interval of at least 12 h between these two doses.

1. Blood sampling should be completed within +/- 30 min of the planned collected time.
2. Blood sampling not performed at this visit may be postponed until the following visits.

## 7.2. Screening and Critical Baseline Assessments

Cardiovascular medical history/risk factors will be assessed (documented in the eCRF) at baseline.

In addition, the following demographic information will be collected:

- Year of birth
- Gender
- Race and ethnic
- Medical history/treatment history/family history will be assessed in relation to the inclusion/exclusion criteria (Section 5.).

Full details of baseline assessments are provided in [Table 13](#).

## 7.3. Efficacy

Efficacy will be assessed according to the Time and Event Table ([Table 13](#)).

Hgb concentrations measured by the central laboratory will be mainly used for efficacy assessment (see Section 7.4.7.).

GSK will supply a point-of-care Hgb analyzer (HemoCue) to each site for rapid and convenient measurement of Hgb and to ensure consistency of Hgb measurements across all sites participating in the study. Assessment for Hgb concentrations via HemoCue will be used for eligibility (Section 5.1.), withdrawal (Section 5.4.), and dose adjustment criteria (Section 6.4.).

In addition, assessments of iron metabolism parameters and measures of CKD progression (e.g., eGFR) used for efficacy assessment are outlined with specific procedures in Section 7.4.7..

## 7.4. Safety

Planned time points for all safety assessments are listed in the Time and Events Table ([Table 13](#)).

Additional time points for safety tests (such as vital signs, physical exams and laboratory safety tests) may be added during the course of the study based on newly available data to ensure appropriate safety monitoring.

### 7.4.1. Adverse Events (AE) and Serious Adverse Events (SAEs)

The definitions of an AE or SAE can be found in Section 12.6. Appendix 6.

The investigator and their designees are responsible for detecting, documenting and reporting events that meet the definition of an AE or SAE.

**7.4.1.1. Time period and Frequency for collecting AE and SAE information**

- AEs and SAEs will be collected from the start of Study Treatment until the follow-up contact (see Section 7.4.1.3.), at the timepoints specified in the Time and Events Table (Table 13).
- Medical occurrences that begin prior to the start of study treatment but after obtaining informed consent may be recorded on the Medical History/Current Medical Conditions section of the CRF.
- Any SAEs assessed as related to study participation (e.g., protocol-mandated procedures, invasive tests, or change in existing therapy) or related to a GSK product will be recorded from the time a subject consents to participate in the study up to and including any follow-up contact.
- All SAEs will be recorded and reported to GSK within 24 hours, as indicated in Section 12.6. Appendix 6.
- Investigators are not obligated to actively seek AEs or SAEs in former study subjects. However, if the investigator learns of any SAE, including a death, at any time after a subject has been discharged from the study, and he/she considers the event reasonably related to the study treatment or study participation, the investigator must promptly notify GSK.

NOTE: The method of recording, evaluating and assessing causality of AEs and SAEs plus procedures for completing and transmitting SAE reports to GSK are provided in Section 12.6. Appendix 6.

**7.4.1.2. Method of Detecting AEs and SAEs**

Care will be taken not to introduce bias when detecting AEs and/or SAEs. Open-ended and non-leading verbal questioning of the subject is the preferred method to inquire about AE occurrence. Appropriate questions include:

- “How are you feeling?”
- “Have you had any (other) medical problems since your last visit/contact?”
- “Have you taken any new medicines, other than those provided in this study, since your last visit/contact?”

**7.4.1.3. Follow-up of AEs and SAEs**

After the initial AE/SAE report, the investigator is required to proactively follow each subject at subsequent visits/contacts. All SAEs, and non-serious AEs of special interest (as defined in Section 7.4.2.) will be followed until resolution, until the condition stabilizes, until the event is otherwise explained, or until the subject is lost to follow-up (as defined in Section 5.4.). Further information on follow-up procedures is given in Section 12.6. Appendix 6..

**7.4.1.4. Cardiovascular and Death Events**

For any cardiovascular events detailed in Section 12.6. Appendix 6 and all deaths, whether or not they are considered SAEs, specific Cardiovascular (CV) and Death sections of the CRF will be required to be completed. These sections include questions regarding cardiovascular (including sudden cardiac death) and non-cardiovascular death.

The CV CRFs are presented as queries in response to reporting of certain CV MedDRA terms. The CV information should be recorded in the specific cardiovascular section of the CRF within one week of receipt of a CV Event data query prompting its completion.

The Death CRF is provided immediately after the occurrence or outcome of death is reported. Initial and follow-up reports regarding death must be completed within one week of when the death is reported.

#### **7.4.1.5. Regulatory Reporting Requirements for SAEs**

Prompt notification by the investigator to GSK of SAEs and non-serious AEs related to study treatment (even for non- interventional post-marketing studies) is essential so that legal obligations and ethical responsibilities towards the safety of subjects and the safety of a product under clinical investigation are met.

GSK has a legal responsibility to notify both the local regulatory authority and other regulatory agencies about the safety of a product under clinical investigation. GSK will comply with country specific regulatory requirements relating to safety reporting to the regulatory authority, Institutional Review Board (IRB)/Independent Ethics Committee (IEC) and investigators.

Investigator safety reports are prepared for suspected unexpected serious adverse reactions according to local regulatory requirements and GSK policy and are forwarded to investigators as necessary.

An investigator who receives an investigator safety report describing a SAE(s) or other specific safety information (e.g., summary or listing of SAEs) from GSK will file it with the IB and will notify the IRB/IEC, if appropriate according to local requirements.

#### **7.4.2. Adverse Events of Special Interest**

The investigator (or subinvestigator) or designee will be responsible for detecting, documenting, and reporting any AEs of special interest listed below. These events have been identified based on the known safety profiles of ESAs, theoretical or potential risks based on the mechanism of action of GSK1278863, and findings from completed nonclinical studies of GSK1278863.

- Thrombosis and/or tissue ischemia secondary to excessive erythropoiesis
- Death, myocardial infarction, stroke, venous thromboembolism, thrombosis of vascular access
- Cardiomyopathy
- Pulmonary artery hypertension
- Cancer-related mortality and tumor progression and recurrence
- Esophageal and gastric erosions
- Proliferative retinopathy, macular edema, choroidal neovascularization
- Exacerbation of inflammatory joint disease (e.g., rheumatoid arthritis)

Any relevant AE should be recorded in the relevant section of the subject's eCRF.

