##### **9.4.4.2. Adverse Events**

All AEs will be categorized by the MedDRA system organ class and preferred term to tabulate the number and incidence. All AEs, SAEs, AEs leading to discontinuation of study treatment, and AEs of special interest will be summarized separately. Similar summary will be provided for study treatment-related AEs.

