## 12.2. Appendix 2: Risk Assessment

Potential Risk of Clinical Significance	Summary of Data/Rationale for Risk	Mitigation Strategy
GSK1278863		
Excessive erythropoiesis (polycythemia) leading to thrombosis and/or tissue ischemia	
In animal studies, excessive erythropoiesis attributed to GSK1278863 was associated with vascular congestion, microthrombi, and tissue ischemia in a number of organs.
 
Following review of clinical data received to date, this has not been identified as a safety concern for GSK1278863.
 
Phase 2 dose-ranging studies, and associated statistical and exposure response modelling has informed Phase 3 dose rationale, starting doses, dose levels, and dose adjustment scheme to optimize Hgb management.
	
 
Specific eligibility criteria related to requirements for entry Hgb are detailed in Section 5.1.
 
Hgb will be closely monitored throughout the dosing period as outlined in the Time and Events Table Section 7.1.
 
Specific guidance for dose adjustment, dose interruption, or discontinuation of GSK1278863 based on achieved Hgb is provided in Section 6.4.1.
 
These risks have been identified as AEs of special interest and will be monitored instreamly by the internal safety review team throughout the study period.
 

Risk of death, MI, stroke, congestive heart failure, venous thromboembolism, thrombosis of vascular access at Hgb levels which are within the normal range (i.e. not polycythemic conditions)	
Marketed rhEPO/ESAs have been associated with an increased risk for death and serious cardiovascular events when used in patients with anemia of CKD.
 
Following review of clinical data received to date, this has not been identified as a safety concern for GSK1278863.
	
 
Specific eligibility criteria related to CV risk are outlined in Section 5.2.
 
Hgb will be closely monitored throughout the dosing period as outlined in the Time and Events Table Section 7.1.
 
These risks have been identified as AEs of special interest and will be monitored instreamly by the internal safety review team throughout the study period.
 

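### Appendix 2 calls congestive heart failure an adverse event of special interest, but the Section 7.4.2 list that the follow-up rule cites omits it

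*Protocol*

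**What the plan says.** Section 7.4.2 makes the investigator "responsible for detecting, documenting, and reporting any AEs of special interest listed below". The cardiovascular line of the list is "Death, myocardial infarction, stroke, venous thromboembolism, thrombosis of vascular access". The only other cardiac entry is "Cardiomyopathy". Heart failure appears nowhere in the list.

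Appendix 2 (Section 12.2) has a risk row headed "Risk of death, MI, stroke, congestive heart failure, venous thromboembolism, thrombosis of vascular access at Hgb levels which are within the normal range". Its mitigation column lists cardiovascular eligibility criteria, Hgb monitoring, and this statement: "These risks have been identified as AEs of special interest and will be monitored instreamly by the internal safety review team".

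Two other sections use the AESI category:
- Section 7.4.1.3, on follow-up: "All SAEs, and non-serious AEs of special interest (as defined in Section 7.4.2.) will be followed until resolution".
- Section 9.4.4.2, on tables: "All AEs, SAEs, AEs leading to discontinuation of study treatment, and AEs of special interest will be summarized separately".

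Section 12.6.3 separately lists congestive heart failure, serious or not, among the events that require the cardiovascular CRF page.

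**The concern.** The same cardiovascular line appears twice in the current text, once with heart failure and once without, and the rules downstream depend on the shorter one. A site that follows 7.4.1.3 literally has no instruction to follow a non-serious heart failure event to resolution. A programmer who builds the AESI table from 7.4.2 would not include heart failure as a term.

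The event is plausible in this trial. Exclusion criterion 7 bars only NYHA Class IV, so subjects in Classes I to III may enter, with stage 3 to 5 CKD or on peritoneal dialysis, for 52 weeks of treatment. Section 4.6.2 also suggests that the study drug may raise Hgb without adding cardiovascular risk. An AESI comparison without heart failure would leave part of that suggestion unexamined under the AESI heading. Section 4.6.1 refers to Appendix 2 for the risk-minimisation measures, and Section 4.6.3 relies on them for its favourable conclusion, so what Appendix 2 says about AESI status should agree with the operative section.

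**Working it through.** No figure is involved. The check compares the two texts and traces which rules use the definition.

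**Item by item**

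| Item | Appendix 2 cardiovascular row | Section 7.4.2, second bullet |
|---|---|---|
| Death | yes | yes |
| Myocardial infarction | yes | yes |
| Stroke | yes | yes |
| Congestive heart failure | yes | **no** |
| Venous thromboembolism | yes | yes |
| Vascular access thrombosis | yes | yes |

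Appendix 2 has six items and 7.4.2 has five, in the same order. The one difference is heart failure.

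**Is the 7.4.2 list closed?** Yes. It refers to the events listed below it, and nothing marks the list as a whole as illustrative.

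**Does another 7.4.2 entry cover heart failure?** Not in general. Cardiomyopathy has its own row in Appendix 2, with a rationale based on HIF stabilisation, so the protocol treats it as a separate risk.

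**Do the other rows agree?** Appendix 2 has eight clinical-event rows. Seven match a 7.4.2 bullet in substance. Only the cardiovascular row loses an item.

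**Where the definition is used**
1. Follow-up (7.4.1.3) cites 7.4.2 by number. Serious heart failure is covered as an SAE. Non-serious heart failure is neither an SAE nor on the list, so the until-resolution rule does not reach it. This link is explicit.
2. AESI summary (9.4.4.2) does not cite 7.4.2. The link is inferred, because 7.4.2 is the only AESI definition in the protocol as shown. On that reading, non-fatal heart failure is left out, while a fatal case enters through the death entry.

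**Subjects concerned.** Cohort 1 randomises 135 to the study drug and 135 to control. Cohort 2 adds 50 PD subjects on the study drug without a control, giving 135 + 50 = 185 planned on the study drug. Section 9.4.4 reports safety by cohort and treatment group, so the comparison is 135 against 135. The protocol gives no heart failure rate, so no event count can be derived.

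**The case against.** **The slip may be in Appendix 2.** The AESI sentence recurs there almost as standard wording. It even closes the drug-drug interactions row, which has no counterpart in 7.4.2. The ESA control row refers back to the same cardiovascular risk and also leaves out heart failure. This stands in part: the direction of the error is likely but not proven. The counter-evidence is not strong, however. An interaction is not an adverse-event term, whereas heart failure is. The ESA row also drops death, which 7.4.2 does list, so that row is simply abbreviated. Either way, one of the two passages is wrong.

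**A reader might infer that the stated mitigation for this risk is not carried out.** The protocol does not support that. Eligibility criteria and Hgb monitoring do not depend on 7.4.2, and the in-stream review is promised in Appendix 2 itself without reference to 7.4.2.

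**A reader might infer that all heart failure events in 185 and 135 subjects drop out of the AESI table.** This goes too far. Those are planned enrolments, not events, and 185 pools a randomised arm with a single-arm cohort. Fatal cases count under death, and a case reported as cardiomyopathy falls under that entry. The reporting and analysis plan, not shown, may also define the AESI terms.

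**The follow-up gap is narrow.** This stands. Section 7.4.1.3 also contains a general duty to keep following each subject at later visits after an event is reported. Heart failure that requires hospitalisation is an SAE. AEs are collected until the follow-up contact. What is missing is the explicit until-resolution requirement for non-serious cases, and an analysis plan could not restore follow-up that a site was never asked to do.

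**Conclusion.** The inconsistency is real and lies within the Amendment 01 text. The unamended text, also in the file, has the same mismatch. As written, non-serious heart failure is outside the until-resolution follow-up rule; that follows directly from the cross-reference. Non-fatal heart failure would probably be absent from the separate AESI summary; that rests on the assumption that no other document supplies a wider definition.

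The size is modest. Event records are not lost, because all cases reach the cardiovascular CRF page and the all-AE tables, and serious ones the SAE tables. The number of affected events is unknown. The primary analysis is untouched. The point is still more than clerical, because it changes what sites are asked to follow and how a named cardiovascular risk is classified, and it should be corrected.

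**What to change.** Reconcile Section 7.4.2 with Appendix 2. The simplest change is to add congestive heart failure to the second bullet of 7.4.2, so that the follow-up rule in 7.4.1.3 and the AESI summary in 9.4.4.2 agree with the risk assessment. If the sponsor does not intend heart failure to be an AESI, amend the statement in the Appendix 2 cardiovascular row instead.

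The first option costs a few words and one row in the AESI table. It needs no new visit or CRF page, since Section 12.6.3 already collects the event. The second option costs one edited sentence in Appendix 2.
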